- 12 Current diagnosis of a comorbid condition known to be associated with other forms of arthritis or joint pathology other than OA, including but not necessarily limited to immunological or autoimmune diseases (eg, RA, lupus erythematosus, inflammatory bowel disease, Crohn's disease, ulcerative colitis, ankylosing spondylitis); seronegative spondyloarthropathies; or other diseases involving the target joint (including endocrinopathies, metabolic joint diseases, joint infections, Paget's disease, or tumours)

Note: Non-OA causes of pain in the target knee such as anserine or patellar bursitis are exclusionary.

- 13 The following conditions (based on screening imaging results as per central reader evaluation) should be excluded: RPOA, primary osteonecrosis (including spontaneous osteonecrosis of the knee), SIF, avascular necrosis, osteoporotic fractures, hip dislocation, pathological fractures, or stress fracture or reaction.
- 14 History of significant trauma (eg, intra-articular fracture) to a knee, hip, or shoulder within 1 year prior to screening or between screening and randomisation.
- 15 Participants who, in the opinion of the investigator, are not suitable candidates for joint replacement surgery
- 16 Presence of neuropathic pain (except for pain related to tunnel neuropathies in upper limbs), or chronic primary pain syndromes (per the eleventh edition of the International Classification of Diseases): eg, fibromyalgia.
- 17 Presence of OA of other major joints (including but not limited to nontarget knee joint) that could interfere with assessment of pain due to OA of the target knee
- 18 Presence of clinically significant neuropathy (eg, hereditary, autonomic or inflammatory neuropathy).

Note: entrapment/tunnel neuropathy affecting the upper limbs that is considered stable is not necessarily excluded; sensory neuropathy that is considered stable and

non-progressive for at least 6 months is not necessarily excluded. Note: for non-exclusionary neuropathies, there is a requirement for participants to undergo a baseline evaluation by a neurologist and to have relevant nerve conduction studies conducted and documented at baseline.

- 19 Requires wheelchair for mobility
- 20 History or current diagnosis of
 - # Severe major depression
 - # Psychotic disorders
 - # Somatoform disorders
 - # Bipolar disorders
 - # Suicidal attempts
 - # Hospital admission for depression within 5 years prior to screening

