7.1.1 Subject-specific Criteria for Discontinuation of Investigational Product

For any individual participant, further administration of IP will be stopped if any of the following scenarios occur:

- # Reports of drug-related SAE(s) or drug-related AE(s) including but not necessarily limited to:
 - Serious or severe drug-related injection site reactions
 - Anaphylactic reaction, defined as an immediately life-threatening allergic reaction with bronchoconstriction, angioedema, and/or hypotension (FDA 2014); or serious hypersensitivity reactions
 - Development of moderate-to-severe sensory abnormalities (eg, paraesthesia, dysesthesia, burning, pins and needles) that are not resolved within a 14-day period
 - Development of peripheral neuropathy
 - New onset of demyelinating disorder
 - Serious systemic infection
 - o Serious non-systemic infection if deemed necessary by the investigator

- # Any of the following are criteria for immediate and permanent discontinuation of IP (Section 8.2.11.1):
 - \circ ALT or AST > 5 × ULN for more than 2 weeks
 - ALT or AST ≥ 3 × ULN and coexisting total bilirubin ≥ 2 × ULN (Hy's Law [HL]). Hy's law is described in Section 8.3.8 and FU of HL cases is provided in Appendix F.
 - \circ ALT or AST \geq 3 × ULN and coexisting international normalised ratio (INR) > 1.5
 - ALT or AST ≥ 3 × ULN and associated with symptoms (which may be either transient or persistent) of hepatitis or hypersensitivity. Hepatitis symptoms include fatigue, nausea, vomiting, right upper quadrant pain or tenderness. Hypersensitivity symptoms include eosinophilia (≥ 5%), rash, or fever without clear alternative cause.
 - Any change in ALT or AST level (eg, < 3 × ULN) if there is a possibility of development of autoimmune hepatitis as per investigator's judgement. Participant should have a consult with a hepatologist, and liver chemistry values, as well as additional tests, should be completed as soon as possible (Appendix F 7)
- # AEs suggestive of autonomous nervous system dysfunction, including but not limited to confirmed orthostatic hypotension (Section 8.2.3.2) or significant bradycardia (Section 8.2.4) or syncope that after evaluation by a cardiologist (and/or neurologist) are considered to be a manifestation of sympathetic autonomic dysfunction
- # Cases when sympathetic neuropathy is not confirmed but orthostatic hypotension remains symptomatic for more than 14 days

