7.1.3 Temporary Discontinuation of Investigational Product

Withholding IP administration temporarily may be considered in the following cases:

- ∀ Development of sensory abnormalities (eg, paraesthesia, dysesthesia, burning, pins and needles) to confirm their resolution within 14 days prior to the next IP administration
- ∀ AE suggestive of new occurrence or worsening of peripheral neuropathy
- ∀ Participants who have the following sympathetic function AEs (any seriousness or severity):
 - # Meet the prespecified criteria for bradycardia (Section 8.2.4)
 - # Meet the prespecified criteria for confirmed orthostatic hypotension (Section 8.2.3.2)
 - # Have syncope
 - # Report anhidrosis or hypohidrosis
- ∀ Cases where additional evaluation or adjudication is needed to exclude possible or probable RPOA, SIF, primary osteonecrosis (including spontaneous osteonecrosis of the knee), or pathological fracture.

- ∀ Cases of signs/symptoms suggestive of worsening or new occurrence of heart failure
- ∀ When follow-up on cases of abnormal liver function is needed before the decision on permanent IP discontinuation is made (eg, identification of potential HL (PHL) cases needed or further evaluation in order to exclude HL required, or ALT or AST ≥ 5 × ULN for less than 2 weeks)
- \forall A positive test for SARS-CoV-2 at any time point during participation in the study.
- ∀ Symptoms or signs consistent with COVID-19 infection (eg, fever, cough, dyspnoea), confirmed by an appropriate laboratory test.

Participants who meet criteria for bradycardia, orthostatic hypotension, who have had a syncope, or report anhidrosis or hypohidrosis should be evaluated by a cardiologist or neurologist as soon as possible.

Participants with AEs suggestive of new occurrence or worsening of peripheral neuropathy as per investigator's neurological assessment should be evaluated by a neurologist as soon as possible.

Participants with clinical signs/symptoms suggestive of worsening or new occurrence of heart failure should be evaluated by a cardiologist as soon as possible. Echocardiography should be performed if clinically indicated. The participant should not be dosed with the subsequent dose of IP until (if applicable) the absence of sensory abnormalities, sympathetic dysfunction, new occurrence or worsening of peripheral neuropathy or Class 3 or Class 4 (NYHA 1994) heart failure have been confirmed, or RPOA, SIF, primary osteonecrosis, or pathological fracture have been excluded.

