Please refer to the Appendix F for guidance on follow-up procedures for PHL and HL cases and Section 8.2.11.1 for management of other cases of abnormal liver function.

Administration of IP can be resumed if deemed appropriate by the investigator in participants with fully resolved asymptomatic or mild COVID-19 infection (confirmed by negative SARS-CoV-2 testing (ie, antigen-based), suggesting that the participant is no longer carrying replicating virus) provided that it is completely resolved without sequalae within 28 days since the previous IP administration and participants do not require ongoing treatment for COVID-19 infection as well as do not have ongoing adverse drug reactions associated with treatment of COVID-19 infection as assessed by the investigator. Additionally, more than 5 half-lives of COVID-19 antiviral medications should elapse before IP administration is resumed. Participants who were treated with anti-SARS-CoV-2 monoclonal antibodies are not eligible for further IP administration. For participants treated with COVID-19 antiviral medications, the investigator should contact the medical monitor and agree if and when further IP administration is appropriate.

If more than 28 days have elapsed since the last IP administration, IP should be permanently discontinued. The participants will be asked to complete the ET visit as soon as possible and then enter the FU period. Refer to the SoA (Table 1) for assessments to be performed at the ET visit and FU period and to Section 7.1.2 for procedures for early discontinuation of IP.

If less than 28 days have elapsed since the last IP administration and once the above mentioned events have been evaluated/adjudicated as not meeting individual discontinuation criteria (and the participant does not meet any other IP discontinuation criteria), IP should be administrated as soon as possible. The participant should be brought back to the study schedule as soon as feasible using the allowed visit windows (provided the interval between subsequent IP administrations is not shorter than 8 days).

7.1.4 **Procedures for Handling Incorrectly Enrolled or Randomised Subjects**

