8.2.2 Neurological Examinations

The neurological examination should be performed by a neurologist or an appropriately experienced physician and will include assessment of mental status, cranial nerves, motor examination (muscle strength and tone), upper and lower extremity deep tendon reflexes, plantar responses, sensory system examination, coordination, and gait. Also information about presence of anhidrosis or hypohidrosis should be collected during the examination.

Ideally, the neurological examination should be performed by the same examiner at each clinic visit.

A neurologic evaluation should be performed by a consulting neurologist if any of the following occurs:

- \forall An AE suggestive of new occurrence or worsening of peripheral neuropathy
- ∀ AE of new occurrence or worsening of abnormal sensation such as allodynia, burning sensation, dysesthesia, hyporesthesia, neuralgia, paresthesia, or sensory loss
- ∀ A new or worse clinically significant abnormality on the neurological exam (in addition to the guidance above)
- \forall A neurological AE considered medically important by the investigator

If the participant experiences any of the events above, a neurological examination by a consulting neurologist should be obtained as soon as possible (including a nerve conduction velocity test if deemed necessary by the neurologist) after these signs and symptoms are identified.

For participants with clinical manifestations consistent with worsening of pre-existing neuropathy, follow-up nerve conduction studies should be performed and documented at the time points deemed appropriate by the neurologist, but at least once during participation in the study. The results should be recorded in the appropriate eCRF. Adverse events should be reported where applicable as described in Section 8.3 and Appendix C.

The participant should not be dosed with the subsequent dose of IP until the absence of the neurological condition that meets prespecified criteria for IP discontinuation has been confirmed. Refer to Section 7.1.1 for prespecified criteria for discontinuation of IP and Section 7.1.3 for temporary discontinuation of IP.

Cases of anhidrosis or hypohidrosis should be further evaluated by a neurologist (or another relevant specialist trained in the assessment of autonomic nervous function, eg, cardiologist) to exclude presence of sympathetic autonomic neuropathy as soon as possible.

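### Section 7.1.3 conflicts with itself and with Section 8.2.2 on re-dosing after a mild sensory abnormality that does not resolve, and Section 7.1.1 is silent on worsening of an allowed neuropathy

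*Protocol*

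**What the plan says.** **Section 7.1.3** lists situations in which withholding a dose may be considered. They include newly developed sensory abnormalities and AEs that suggest new or worsened peripheral neuropathy. It then gives a direct instruction: "The participant should not be dosed with the subsequent dose of IP until (if applicable) the absence of sensory abnormalities" has been confirmed. The same sentence requires that new or worsened peripheral neuropathy be excluded. Two timing rules follow. The first is "If more than 28 days have elapsed since the last IP administration, IP should be permanently discontinued". The second applies when fewer than 28 days have passed: "once the above mentioned events have been evaluated/adjudicated as not meeting individual discontinuation criteria", the dose is to be given as soon as possible.

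**Section 7.1.1** holds the individual discontinuation criteria. Under the stem "Reports of drug-related SAE(s) or drug-related AE(s) including but not necessarily limited to", the sensory entry is "Development of moderate-to-severe sensory abnormalities (eg, paraesthesia, dysesthesia, burning, pins and needles) that are not resolved within a 14-day period" and the neuropathy entry is "Development of peripheral neuropathy".

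**Section 8.2.2** withholds the next dose "until the absence of the neurological condition that meets prespecified criteria for IP discontinuation has been confirmed" and refers the reader to both 7.1.1 and 7.1.3. Where a pre-existing neuropathy worsens clinically, it asks for follow-up nerve conduction studies and states no stopping rule.

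**Section 5.2**, criterion 18, lets some neuropathies in. A sensory neuropathy that is stable and "non-progressive for at least 6 months is not necessarily excluded", and stable upper-limb entrapment neuropathy is treated the same way.

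**Section 9.4.2.1** imputes the primary endpoint as return to baseline when data are missing because of discontinuation for an AE, and as missing at random when discontinuation is for other reasons. Under Section 8.1.1, daily pain recording ends at the early termination visit for anyone who stops treatment early.

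**The concern.** These instructions decide whether a participant receives the next injection. Abnormal sensation is a recognised risk of the class: Section 2.3.1.1 reports that such AEs were more frequent on an anti-NGF antibody than on placebo or active comparator. Section 2.3.1.4 relies on neurological follow-up and individual stopping criteria to contain that risk. If the sections disagree, two sites can each follow the Protocol and treat the same event differently.

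The choice also carries into the primary analysis. A participant who is dosed again can supply an observed Week 12 score. One who is stopped has no Week 12 diary data, and the imputation then depends on the recorded reason for stopping. If such events are more common on active drug, uneven handling would not be balanced across arms.

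**Working it through.** The Protocol gives no figure to reproduce on this point, so the check sets the texts side by side.

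**Case A: mild sensory abnormality that persists**

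| Text | Next dose |
|---|---|
| 7.1.3, dosing block | No, until absence is confirmed; any severity |
| 7.1.3, 28-day rule | Permanent stop once the hold runs past 28 days |
| 7.1.3, release rule | Yes, if the 7.1.1 criteria are not met and fewer than 28 days have passed |
| 7.1.1, sensory entry | Not met; the entry covers moderate-to-severe only |
| 8.2.2, dosing block | Yes; the condition does not meet a discontinuation criterion |

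Doses are 14 days apart, so a timeline can be drawn. Count days from the last dose and suppose that mild paraesthesia starts on day 5 (an assumed date) and does not clear.

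- Dosing block: the doses due on days 14 and 28 are withheld, and from day 29 the stop is permanent.
- Release rule: the participant is evaluated, the event does not match the 7.1.1 sensory entry, and the next dose is given, subject to the 8-day minimum gap.

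Both outcomes come from Section 7.1.3. The words in brackets in the block select which listed condition is in play and add no severity threshold. The permissive opening of 7.1.3 makes starting a hold optional, but the later sentence is an instruction.

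**Case B: confirmed worsening of a neuropathy allowed under criterion 18**

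| Text | Next dose |
|---|---|
| 7.1.3, dosing block | No, until worsening is excluded |
| 7.1.3, release rule | Depends on 7.1.1 |
| 7.1.1, neuropathy entry | Names development only; silent on worsening |
| 8.2.2, dosing block | Depends on 7.1.1 |

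The block is explicit. The other two routes lead to a list that does not name the event, so the answer turns on whether the site reads worsening into the open stem of 7.1.1.

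**Consequence for the primary score**

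- Stop recorded as due to an AE: mean change imputed at zero (return to baseline).
- Stop recorded under other reasons: missing-at-random imputation.
- Dosed again and completing: observed Week 12 change.

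**Illustration of size, on assumptions that are not in the Protocol.** Let a share p of an active arm move from an average observed change to a mean change of zero. Let placebo improve by c points, and let the true difference be 1.5 (Section 9.2). The affected participants would otherwise have improved by c + 1.5, so the difference becomes 1.5 − p × (c + 1.5).

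| p | c = 1 | c = 3 |
|---|---|---|
| 2% | 1.5 − 0.02 × 2.5 = 1.45 | 1.5 − 0.02 × 4.5 = 1.41 |
| 5% | 1.5 − 0.05 × 2.5 = 1.375 | 1.5 − 0.05 × 4.5 = 1.275 |
| 10% | 1.5 − 0.10 × 2.5 = 1.25 | 1.5 − 0.10 × 4.5 = 1.05 |

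For any given p, the table compares every affected participant handled one way with every one handled the other way. It also assumes no such events on placebo and AE coding of every stop. Mixed handling between sites would move the difference less.

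**The case against.** The strongest reply is that Section 7.1.3 can be read in sequence: hold while the event is evaluated, then release against the 7.1.1 criteria. Sections 7.1.1 and 8.2.2 agree with each other in the mild case, so most of the text points one way. That stands as far as it goes, and it rules out saying that the three sections give three opposite answers. It does not remove the conflict. The dosing block asks for confirmed absence of the abnormality, not for completed evaluation, and the 28-day rule gives that wording a permanent consequence.

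On worsening of an allowed neuropathy, a reader might infer that 7.1.1 permits re-dosing. It does not say so. Its list is open-ended, and Section 7.1 separately stops treatment for an AE that the investigator considers a contraindication to further dosing. Section 7.1.1 is silent, and what remains is investigator judgement informed by a neurologist. The mismatch with the explicit block in 7.1.3 still needs an answer.

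Two further readings are tempting and should not be pressed. One is that a participant admitted with a stable sensory neuropathy could never satisfy the block. The trigger in 7.1.3 is the development of sensory abnormalities, so a stable pre-existing condition need not start a hold. The other is that the 7.1.1 stem stops treatment for any drug-related AE. That would make the thresholds in its own entries pointless.

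The objection to any firm effect on the primary result also stands. The group is narrow: the event must start before the last dose at Week 10 and must meet no listed criterion. The Protocol does not say how a stop forced by the 28-day rule is coded. Clustering in the higher-dose arms is extrapolated from another antibody, and Section 2.2.2 reports no clinically significant changes or dose-related trends in neuropathy assessments in this product's own osteoarthritis study.

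**Conclusion.** The point holds as a contradiction in dosing instructions. For a mild sensory abnormality that does not resolve, the block in 7.1.3 conflicts with the release rule in 7.1.3 and with Section 8.2.2. For worsening of an allowed neuropathy, 7.1.3 blocks dosing while the criteria to which 8.2.2 defers do not address it. This rests on the current wording alone and needs no assumption.

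The link to the primary endpoint is conditional. The scores differ if a stop is recorded as due to an AE and the re-dosed participant reaches Week 12. A reader might infer a stated percentage loss of the 1.5-point effect, or a distorted dose-response curve. The Protocol supports neither, because it gives no rate for these events, no split by arm and no coding for a 28-day stop. The size is unknown. The case for correcting the text is consistent safety handling of a known class risk.

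**What to change.** Reconcile four pieces of text so that they give one instruction: the dosing block in 7.1.3, the release rule in 7.1.3, the criteria in 7.1.1 and the block in 8.2.2. The reconciled text should answer two questions the same way wherever they arise:

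- whether a mild sensory abnormality that does not resolve prevents the next dose;
- how confirmed worsening of a pre-existing neuropathy allowed under criterion 18 is handled.

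Which answer is clinically right is for the sponsor to decide. The cost is Protocol wording and a letter to sites. No new assessment is needed, because neurologist evaluation, and baseline nerve conduction studies for participants admitted with a neuropathy, are already required.

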7.2 Subject Withdrawal from the Study

- ∀ A participant may withdraw from the study at any time at his/her own request, or may be withdrawn at any time at the discretion of the investigator for safety, behavioural, compliance, or administrative reasons. This is expected to be uncommon.
- ∀ A participant who considers withdrawing from the study must be informed by the investigator about modified FU options (eg, telephone contact, a contact with a relative or treating physician, or information from medical records).
- ∀ At the time of withdrawal from the study, if possible, an ET visit should be conducted as described in the SoA (Table 1). Participants who have received at least one dose of IP are expected to complete study assessments at the ET visit as soon as possible and then to enter the FU period (Section 7.1.2).
- ∀ If the participant withdraws consent for disclosure of future information, the sponsor may retain and continue to use any data collected before such a withdrawal of consent.
- ∀ If a participant withdraws from the study, it should be confirmed if he/she still agrees for existing samples to be used in line with the original consent. If he/she requests withdrawal of consent for use of samples, destruction of any samples taken and not tested should be carried out in line with what was stated in the informed consent and local regulation. The investigator must document the decision on use of existing samples in the site study records and inform the Global Study Team.

Investigators must attempt to contact participants who fail to attend scheduled visits by telephone or other means to exclude the possibility of an AE being the cause of withdrawal. Should this be the cause, the AE must be documented, reported, and followed as described in Section 8.3.

7.3 Lost to Follow-up

A participant will be considered lost to FU if he or she repeatedly fails to return for scheduled visits and is unable to be contacted by the study site.

To prevent a participant being lost to FU, it is recommended that the study sites maintain upto-date contact details for participants, including next of kin or other emergency contacts (if allowed by national regulation).

The investigator should educate the participant on the importance of maintaining contact with the investigator/study site throughout the study.

The following actions must be taken if a participant fails to return to the clinic for a required study visit:

- ∀ The site must attempt to contact the participant and reschedule the missed visit as soon as possible and counsel the participant on the importance of maintaining the assigned visit schedule and ascertain whether or not the participant wishes to and/or should continue in the study.
- ∀ Before a participant is deemed lost to FU, the investigator or designee must make every effort to regain contact with the participant or next of kin/emergency contact by repeated telephone calls, emails and, if necessary, a certified letter to the participant's last known mailing address or local equivalent methods. These contact attempts should be documented in the participant's medical record.
- ∀ Should the participant continue to be unreachable, he/she will be considered to have withdrawn from the study with a primary reason of lost to FU. The participant will be classified as lost to FU only if he/she has failed to return for the required study visits and his/her vital status remains unknown at the end of the study (ie, Week 36) despite all the above listed efforts. For the primary analysis purposes, a participant will be classified as lost to FU if he/she has failed to return for the required study visits and his/her vital status remains unknown at the time of primary database lock (ie, after the Week 36 visit).
- ∀ Site personnel will attempt to collect the vital status of the participant within legal and ethical boundaries for all participants randomised, including those who did not receive IP. Public sources may be searched for vital status information. If vital status is determined as deceased, this will be documented, and the participant will not be considered lost to FU. AstraZeneca personnel will not be involved in any attempts to collect vital status information.

Discontinuation of specific sites or of the study as a whole is handled as part of Appendix B.

